8. DATA MANAGEMENT

8.1 Data Collection

A trained member of the research team will obtain age (years), sex, height (cm), and weight (kg), as well as the pre screening form (see attached screening checklist, 16.3). This data will then be uploaded to the sync.com account and completed, if necessary, by [name].

[name] will administer the ImPACT and BESS. ImPACT results will be recorded and stored on the secured, password protected, ImPACT Applications, Inc. server. Data will be immediately coded by the researcher. BESS computer data will stored on a secure, password protected computer in [name] secure office (currently SB-1009).

[name] will oversee the collection of the saliva sample at the School of Kinesiology, Lakehead University. The research assistant will label the tube with the participant code and will transport it back to NOSM (unless already at NOSM), where it will be immediately processed.

Oddball and Flanker tasks will be overseen by [name] and [name]. All data will be collected and analyzed in [name] Laboratory at Lakehead University.

The driving simulation will be overseen by [name] at the Centre for Research on Safe Driving and recorded by the STISIM Drive[®] Model 400 driving simulator.

8.2 Data Management

The research team (Principal Investigator, Co-Investigators and research assistant) has access to all data if necessary. The research assistant will create a code key that will be kept on a secure Sync.com account (see below for further information, access provided through NOSM) in an encrypted file, along with the electronic coded data abstraction files. These files will be kept separate from the code key in order to prevent participant identification.

The hard copy screening checklists will be coded and stored in [name] current office in a locked filing cabinet at School of Kinesiology, Lakehead University (SB-1007). Electronic copies will be uploaded to the secure Sync.com account.

Saliva samples will be immediately coded and processed/stored in the NOSM laboratory. Results of the saliva analysis will be stored in an encrypted file on a password protected computer in a secure office.

[name] will extract ImPACT data from the ImPACT Applications, Inc. server to a password protected computer in a secure office. Electronic data collected from the BESS will be transferred to a secure USB (for data transfer) and then to a password protected computer in a secure office. All paper and electronic data will be coded and uploaded to the secure Sync.com account.

Electronic data collected from the Oddball and Flanker tasks will be coded to a secure USB (for data transfer) and transferred to a password protected computer in a secure office. Data will then be uploaded to the secure Sync.com account.

Electronic Data collected from the driving simulation will be coded and transferred to a secure USB (for data transfer) and then to a password protected computer in a secure office. Data will then be uploaded to the secure Sync.com account.

Sync.com account details:

The website states the following:

Sync's unique, zero-knowledge storage platform guarantees your privacy by providing end-to-end encryption, and most importantly - only you have access to the encryption keys. We can't read your files. Neither can the NSA.

- Zero-knowledge, end-to-end encryption
- Privacy guarantee (we can't access your files or file metadata)
- 2048 bit RSA, 256 bit AES, SSL and TLS encryption
- Files encrypted in transit and at rest
- Share controls, permissions and user administration
- Remote logout

- Remote wipe
- File audit logs
- Account notifications
- Two-factor authentication

9. SPECIMEN MANAGEMENT

A research assistant, will facilitate the collection of the saliva following an establish passive drool protocol. Participants will be instructed to drool through a straw into a collection tube. The samples will be transported Lakehead University School of Kinesiology to NOSM for processing and analysis. Salivary BDNF will be quantified using an established protocol in [name] lab, which utilizes an enzyme-linked immunosorbent assay. All samples will be labeled with the participant code number as well as a letter for each time point. For example, A for pre-treatment, B for post-treatment. Samples will be kept until all analysis is completed, after which all labels will be removed and samples will be disposed of as biohazardous waste.

10. DATA / SPECIMEN ANALYSIS

[name] and the NOSM research assistant will be performing data analysis on the saliva samples at NOSM. [name], [name], [name], and [name] will be performing analysis on the physical and cognitive measures at Lakehead University. The main analysis will be a comparison of the pre- and post-outcomes.

[name] will perform the analysis of the data collected related to balance from the AMTI force platform and ImPACT neurocognitive assessment. The AMTI force platform measures the ground reaction forces that are generated by a body standing or moving across the plate. The AMTI force plate is also capable of measuring torques about each axis and has six degrees of freedom, which includes three forces (f_z , f_x , and f_y) and three moments (M_z , M_x , and M_y). All of these measures are fed into an AMTI amplifier and converted to digital signals via an analog to digital converter. The information collected by the force platform is then uploaded into BIOSOFT computer software which allows the researcher to view and analyze data following collection. The BIOSOFT computer software calculates the x and y moments of postural sway which are used to compute the variables of interest and produces graphical representations of this data. Descriptive statistics will be calculated to provide the mean and standard deviations for the variables of interest including the area of the centre of pressure, velocity of centre of pressure, length of centre of pressure, and displacement of centre of pressure. The main objective of the analysis is to compare pre- and post-treatment changes in balance. The ImPACT measures components of cognitive functioning including: attention, concentration, reaction time, memory, processing speed, decision making, problem solving, and response variability. The main objective of this component of the analysis will be to compare pre- and post-treatment changes in composite scores for the variables described.

[name] will perform the analysis on the data collected from the driving simulator. This analysis will include the comparison of people with concussion who will undergo AET to those

going through regular standard of care and healthy control on measures of reaction time for dual and non dual tasking driving events. The analysis will be performed pre and post intervention to examine the interaction effect between group and time on measures of reaction time. The statistical analysis will include descriptive statistics to calculate means and standard deviation for each group for the pre and post test data. A mixed factorial analysis of variance will also be performed with group as the independent factor, time (pre and post intervention) as the repeated measure and reaction times as the dependent variable to examine the effect of the AET.

Preprocessing and analysis may either occur on [name] recording computer using asa-lab software or a separate analysis computer (also password protected) using EEGLab software. Prior to analysis data will be segmented into epochs around each event (trial) presentation. Data will be temporally filtered. Baseline line correction using the 200 ms before the stimulus presentation will be applied. Artifact detection and removal will be applied to remove trials that have been affected by excessive head motion (for example blinking, general body movement). Once preprocess, all the trials from the same condition type will be averaged to create an event-related potential for each condition type. This data, for each participant will be exported for statistical analysis (performed in JASP). Repeated measures ANOVA will be used to determine if there are significant between group and between condition differences.

Missing data will be handled according to the type of data that is missing. For analyses that depend on change (pre- vs post-), if a participant misses an assessment (i.e saliva) we will have to exclude the participant's results for that assessment. If the rest of the assessments were completed pre and post intervention, then they will be included in the data analysis.

There will be no interim analysis.

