2. It is anticipated that AET will result in increased efficiency of neural processing during cognitive tasks in post measures compared to SC and with less difference than compared to HC compared to pre- intervention comparisons. Cognitive efficiency will be measured by the amplitude and latency of two event related electrical potentials associated with attention and conflict monitoring processing.
3. It is anticipated that concussed participants receiving the AET will exhibit improved balance. This will be measured using the force platform centre of pressure area, displacement, and velocity measures while completing the various static stance positions using the BESS protocol.
4. It is anticipated that concussed participants receiving the AET will exhibit increased improvements in salivary BDNF levels, indicative of an improvement in concussion symptoms. Salivary BDNF will be quantified using the BDNF ELISA assay and changes in pre- vs. post-intervention concentrations will be assessed. Additionally, we hypothesize that lower levels of BDNF upon entry to the study will indicate more pronounced concussive symptoms. This relationship will be determined by correlating the pre-intervention BDNF concentration to measures of the post intervention assessments.

5. It is anticipated that concussed participants receiving the AET will exhibit improved reaction times compared to the SC group during dual tasking scenarios to avoid crashing in dangerous traffic situations.

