11.2 Statistical Analysis

The main analysis will be a mixed factorial ANOVA to examine interaction effects between group (AET, SC, and HC) and time (pre- and post-) on measures of ERP, balance, BDNF and reaction time. If an interaction is found between group and time on any of the dependent variables (ERP, balance, BDNF and reaction time), the interaction will be explained using simple main effects. If no interaction is found for any of the dependent variable measures, the main effects for time and groups will be examined by a post hoc analysis to determine differences between groups. We anticipate greater change in the AET group compared to SC and HC group.

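### The ERP model has different factors in Section 10 (group and condition, no time) and Section 11.2 (group by time, no condition): the first cannot show the change in hypothesis 2, and the second does not isolate AET versus SC

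*Combined protocol and SAP*

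**What the plan says.** Hypothesis 2 (Section 2) predicts that neural processing in the AET group will be more efficient "in post measures compared to SC and with less difference than compared to HC compared to pre- intervention comparisons". I read this as two claims: AET is better than SC after the intervention, and the gap between AET and HC is smaller afterwards than before. Efficiency is defined there by the amplitude and latency of two potentials. The Flanker description in Section 7.2 names the N200 and P300.

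Section 10 opens with a general statement: "The main analysis will be a comparison of the pre- and post-outcomes". Its ERP paragraph describes preprocessing, says that "all the trials from the same condition type will be averaged to create an event-related potential for each condition type", and ends with the test: "Repeated measures ANOVA will be used to determine if there are significant between group and between condition differences". Time does not appear in that paragraph. The driving analysis just above it, by contrast, names "time (pre and post intervention) as the repeated measure and reaction times as the dependent variable".

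Section 11.2 sets as the main analysis a "mixed factorial ANOVA to examine interaction effects between group (AET, SC, and HC) and time (pre- and post-) on measures of ERP", along with balance, BDNF and reaction time. Condition is not mentioned. If the interaction is found, "the interaction will be explained using simple main effects"; which simple effects is not stated. If it is not found, the main effects of time and group are examined post hoc. The section expects greater change in AET than in SC and HC, but names no contrast.

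**The concern.** The two sections give the ERP analysis different factors, and neither refers to the other. An analyst who follows the more specific text, the ERP paragraph of Section 10, could report a group effect or a condition effect as the ERP result. A condition effect shows that the brain response differs between trial types, so it confirms that the task worked and says nothing about AET. A group effect without time cannot separate what the groups brought to the trial from what the intervention did. That matters most for HC, who are not randomised. The background in Section 1 itself reports lower amplitude and longer latency after concussion, so a group difference involving HC would be expected even if AET did nothing.

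An analyst who follows Section 11.2 tests change, but must decide without guidance how the several condition averages per participant enter the model. The interaction also spans three groups, only two of which were randomised.

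**Working it through.** **Factors set side by side**

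| Source | Group | Time | Condition | AET-SC contrast on change |
|---|---|---|---|---|
| Hypothesis 2 | AET, SC, HC | yes | not mentioned | implied |
| Section 10, ERP paragraph | yes | not named | yes | no |
| Section 11.2 | AET, SC, HC | yes | not named | not named |

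The shrinking AET-HC gap is a group-by-time contrast, so it cannot be tested without time. The AET-SC difference after the intervention could be a group test at the post visit, but Section 10 does not restrict its test to that visit.

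**Cost of a group test averaged over visits**

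Inputs: two-sided alpha 0.05 and 80% power (Section 11.1). The pre-post correlation ρ is not in the documents; I assume 0.3, 0.5 and 0.7. Let d be the AET-SC difference after the intervention in single-visit SDs, with no true difference at entry and n per arm.

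- Change contrast: z = d / √(2(1−ρ)·2/n).
- Group effect on the two-visit mean: z = (d/2) / √(((1+ρ)/2)·2/n).
- Ratio of second to first: √((1−ρ)/(1+ρ)). Both d and n cancel.

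At 80% power the change contrast has z = 1.96 + 0.84 = 2.80. Power of the group effect is Φ(2.80 × ratio − 1.96):

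| ρ | Ratio | z of group effect | Power |
|---|---|---|---|
| 0.3 | 0.73 | 2.06 | 54% |
| 0.5 | 0.58 | 1.62 | 37% |
| 0.7 | 0.42 | 1.18 | 22% |

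**What the Section 11.2 interaction responds to**

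With two time points, the group-by-time test equals a one-way ANOVA on change scores. I simulated it 40,000 times per scenario with 20 per group (Section 5.2). Effects are in SDs of the change score and are assumed.

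| Mean change AET / SC / HC | Omnibus significant | AET vs SC significant |
|---|---|---|
| 0.5 / 0.5 / 0 | 34% | 5% |
| 0.8 / 0.8 / 0 | 73% | 5% |
| 1.0 / 1.0 / 0 | 90% | 5% |
| 0.8 / 0 / 0 | 72% | 69% |

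Rows two and four agree for a structural reason. The noncentrality is n times the sum of squared deviations of the group means from their average. For 0.8 / 0.8 / 0 the average is 0.533, giving 20 × (0.267² + 0.267² + 0.533²) = 8.5. For 0.8 / 0 / 0 the average is 0.267, giving 20 × (0.533² + 0.267² + 0.267²) = 8.5. The omnibus test cannot tell recovery in both concussed groups from an effect of AET alone; the AET-SC contrast can.

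At 17 per group (20 less the 13% dropout of Section 11.1 is 17.4), the omnibus figures for rows two and four are both 64%, and the contrast gives 5% and 62%. A direct AET-SC contrast has 80% power for a difference of 0.91 SD of change with 20 per group and 0.99 SD with 17.

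**The case against.** The best defence is that Section 11.2 already supplies the right analysis. It calls the group-by-time ANOVA the main analysis, names ERP in it, follows it with simple main effects and expects greater change under AET. Section 10 also opens by making the pre-post comparison its main analysis, and its ERP paragraph is mostly preprocessing with one short closing sentence. Much of this stands.

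A reader might infer that the two descriptions are incompatible. The documents do not support that: both fit in one group-by-time-by-condition model, so this is inconsistent and incomplete specification, not contradiction. A reader might also infer that neither section tests hypothesis 2. That goes too far for Section 11.2. The shrinking AET-HC gap is a group-by-time contrast, and the AET-SC comparison after the intervention is a simple effect that the planned follow-up could supply.

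The power figures of 54%, 37% and 22% need the same care. Section 10 does not say that ERPs are averaged over visits; with time unnamed, the model could be run at each visit or could include time. The figures price one possible reading, and it would be wrong to conclude from them that a real AET effect will probably be missed.

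What the defence leaves unanswered is that the ERP sentence omits time where the neighbouring driving analysis names it, that no text says how condition enters the Section 11.2 model, and that no AET-SC contrast is named. The Section 11.2 fallback also leads back to a group main effect when the interaction is not significant.

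**Conclusion.** The point holds as an unreconciled specification. Section 10 as worded cannot show the pre-to-post change in hypothesis 2. Section 11.2 can, but only through a three-group omnibus interaction that does not isolate the randomised comparison, with follow-up contrasts and the role of condition left open.

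The 54%, 37% and 22% depend on assumed correlations and on averaging over visits. The 73% false lead for an AET-specific reading depends on an assumed equal change of 0.8 SD in AET and SC, none in HC, and 20 completers per group. The qualitative conclusion, that the omnibus test can be driven by HC alone, does not depend on those values. The change should be made because ERP is a named outcome of the main analysis and correcting the text is cheap.

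**What to change.** State one ERP model in both sections, with group, time and condition. For each named component measure (amplitude and latency), make the AET-versus-SC contrast on pre-to-post change the pre-specified treatment test. Make the AET-HC gap, post versus pre, a secondary contrast. Report the between-condition main effect as a check that the task worked, not as an outcome.

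State how condition enters. A difference between trial types is one option. Its drawback is that it cancels any treatment shift common to both trial types, which the hypothesis, being defined on amplitude and latency, could count as improvement. The Flanker trial types are not defined in Section 7.2 and need naming. The sponsor should settle this choice, with the electrode and time window, before the analysts are unblinded.

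The cost is protocol and SAP wording and minor analysis work. No new recordings are needed.

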11. STATISTICAL CONSIDERATIONS

11.1 Sample Size Calculation

A priori power analysis was conducted to determine that we would have 80% power at alpha = .05 (two tailed) to detect a medium to large effect size with 12 participants in each group, leaving room for a 13% dropout rate. We therefore propose 20 participants per group.

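### The complete-case rule limits the AET–SC comparison of change to completers, and this can bias it if loss differs by arm and is related to change

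*Combined protocol and SAP*

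**What the plan says.** Section 10 gives the only missing-data rule. For analyses of change, "if a participant misses an assessment (i.e saliva) we will have to exclude" that person's results for the assessment in question. The exclusion is assessment by assessment: "If the rest of the assessments were completed pre and post intervention, then they will be included in the data analysis". Section 11.2 makes a mixed factorial ANOVA the main analysis. It tests group (AET, SC, healthy control) by time (pre, post) on ERP, balance, BDNF and reaction time.

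The timing of the second assessment is described in several ways:

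- Section 5.1 has all participants reassessed after eight weeks.
- The opening of Section 7.2 places reassessment after the intervention for concussed participants and at eight weeks for healthy controls.
- The end of Section 7.2 places it after completion of 24 sessions for AET, and after eight weeks for SC and healthy controls.

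Section 11.1 gives a single allowance for loss, "leaving room for a 13% dropout rate", not split by arm. No section defines an analysis set, states that AET and SC are analysed as assigned, says how AET participants who attend poorly or stop are handled, or plans a missing-data sensitivity analysis.

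**The concern.** AET against SC is the trial's only randomised comparison. With two time points, the interaction test is a comparison of mean change. Under the Section 10 rule, that mean is taken over people who supplied both values, so randomisation no longer guarantees that the compared groups are alike.

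The design gives reasons to expect uneven loss. AET involves three supervised sessions a week for eight weeks, and SC has no study sessions. Read literally, the end of Section 7.2 provides no second assessment for an AET participant who stops early, and the Section 10 rule would then remove that person from every change analysis. The design also gives reasons to expect loss linked to symptoms. Exercise sessions stop when symptoms are reported (Section 3.1), and simulator data collection ends when a participant cannot continue (Section 7.2). If both features occur together, part of an observed AET–SC difference in change, or part of its absence, could come from who stayed.

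**Working it through.** **1. The plan's own figures.** Section 11.1 starts from 12 per group, allows 13% loss and enrols 20. Inflating 12 for 13% loss gives 12/(1 − 0.13) = 13.8, so 14. Conversely, 20 × 0.87 = 17.4, so about 17 remain. The step from 12 to 20 is not reproduced; that is a separate matter. What is used here is 20 enrolled and 13% loss.

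**2. Loss related to baseline.** The following are assumptions, not figures from the documents:

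- There is no true effect.
- Higher scores are worse, and the SD is 1 at both times.
- The pre–post correlation is r = 0.4 to 0.6.
- SC loses nobody. AET loses a fraction L, all from the worse half at baseline.

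The mean baseline of each half is ±0.798, so AET completers have mean baseline −0.798 × L/(1 − L). Their expected change is (r − 1) times that, so the false difference is (1 − r) × 0.798 × L/(1 − L).

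- L = 0.13: 0.798 × 0.13/0.87 = 0.119. Multiplying by 0.4 gives 0.048 (r = 0.6), and by 0.6 gives 0.072 (r = 0.4).
- L = 0.25: 0.798 × 0.25/0.75 = 0.266. Multiplying by 0.4 gives 0.106, and by 0.6 gives 0.160.

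The sign is positive, towards worse. AET completers start better and regress upwards, so the artefact runs against AET. If the milder participants left instead, it would favour AET.

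**3. Effect on type I error (AET–SC comparison, normal approximation).** SE = √[2(1 − r)(1/n_AET + 1/20)], with n_AET = 20(1 − L).

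| L | r | n_AET | False difference | SE | Ratio | Two-sided type I error |
|---|---|---|---|---|---|---|
| 0.13 | 0.6 | 17.4 | 0.048 | 0.293 | 0.16 | 5.3% |
| 0.13 | 0.4 | 17.4 | 0.072 | 0.359 | 0.20 | 5.5% |
| 0.25 | 0.6 | 15 | 0.106 | 0.305 | 0.35 | 6.4% |
| 0.25 | 0.4 | 15 | 0.160 | 0.374 | 0.43 | 7.1% |

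**4. Baseline adjustment.** When loss depends only on baseline, the regression of post on pre is the same among completers, so the adjusted difference is 0.00. This follows from the assumed mechanism and is not a general guarantee. With equal pre and post variances, adjustment changes the variance from 2(1 − r) to 1 − r², a ratio of (1 + r)/2. That is 70% to 80% of the change-score variance at r = 0.4 to 0.6.

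**5. Loss related to change itself.** Suppose a latent tendency to stay has correlation c with change. Completers' mean change then shifts by c × φ(q)/(1 − loss), where q is the normal quantile of the loss fraction. Units here are SDs of change, and the loss rates are again assumed.

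| AET loss / SC loss | c = 0 | c = 0.3 | c = 0.5 | c = 0.7 |
|---|---|---|---|---|
| 13% / 13% | 0 | 0 | 0 | 0 |
| 20% / 5% | 0 | 0.07 | 0.12 | 0.17 |
| 30% / 10% | 0 | 0.09 | 0.15 | 0.21 |
| 40% / 10% | 0 | 0.13 | 0.22 | 0.31 |

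Simulated type I error (8,000 runs, 20 per arm) was 5.3% at 40%/10% with c = 0, 7.0% at 30%/10% with c = 0.5, 9.0% at 40%/10% with c = 0.5, and 5.1% at 13%/13% with c = 0.5. Bias therefore needs both unequal loss and a link with change, or a mechanism that differs between arms.

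**6. Power.** For a two-sample t-test with 80% power and two-sided alpha 0.05, the detectable standardised difference is 0.91 with 20 per arm and 0.99 with 17 per arm. This scenario has loss in both arms, unlike step 2.

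**The case against.** The strongest reply is that the rule is modest and the numbers are small. It removes results only for the affected assessment and keeps the participant's other complete pairs. SC attends the same assessments as AET, so the assessment burden is equal. At the plan's own 13%, even placing all the loss in one arm and in the worse half moves the type I error by half a percentage point or less, in a direction that makes an AET benefit harder to show. Nothing prescribes an as-treated analysis: exclusion follows from missed assessments, not missed sessions, and AET taken later by SC participants is kept out of the analysis (Sections 5.1 and 12.3). The rise in detectable difference from 0.91 to 0.99 comes from missing post values, and a different model largely does not recover it.

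All of this stands, and it limits the point. A reader might infer that 24 sessions against none is enough to bias the result, that the rule deletes participants altogether, or that SC has no visits. The documents support none of these. What the reply does not answer is that Section 7.2 ties the AET second assessment to completing the sessions, that no analysis set is stated, and that no planned analysis would show whether loss had mattered.

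**Conclusion.** The point holds as a conditional risk to the randomised contrast, and the plan should address it. It does not show that the result will be biased. The size rests on assumptions that the documents can neither confirm nor exclude. It is negligible to small with 13% loss related to baseline, larger at 25%, and as much as 0.31 SD of change under the most uneven and strongly change-related loss examined. The direction is not fixed. The case for acting is that the remedy is cheap, uses data already collected, and adds precision through baseline adjustment. Analysis by assigned arm concerns AET and SC only, because healthy controls are not randomised.

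**What to change.** 1. In Sections 10 and 11.2, define the analysis set for AET against SC as all randomised concussed participants with at least one assessment, analysed by assigned arm whatever their attendance. Data withdrawn at a participant's request under Section 4.6 remain excluded.
2. Replace the exclusion rule with a likelihood-based model for the pre and post values. Use a common baseline mean for AET and SC, an unstructured pre/post covariance, and adjustment for age and sex, which are the minimisation factors. Enter healthy controls as a separate non-randomised reference group with their own baseline mean.
3. Reconcile the end of Section 7.2 with its opening and with Section 5.1, so that AET participants who stop sessions early are also sought for the eight-week assessment.
4. Report loss and its reasons by arm and by assessment. Keep the complete-case ANOVA as a sensitivity analysis, and add a simple missing-not-at-random analysis, for example shifting the unobserved AET post values over a stated range.

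The cost is revised wording, a standard model and some effort to reassess people who stop. The model relies on missing-at-random, so it can still be biased if people leave because of worsening that baseline does not predict; the last sensitivity analysis is there for that reason. It does not restore the power lost to missing post values. Its gain in precision comes mainly from baseline adjustment.
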